6.2. Subject Inclusion Criteria

All subjects must meet the following inclusion criteria:

1. Subjects who are able to understand and sign an informed consent document.
2. Subjects 18 years of age or older.
3. Subjects must be diagnosed with PMF, PPV-MF or PET-MF, according to the investigator's expert judgment, guided by the criteria outlined in the 2008 World Health Organization criteria (see Appendix 1) for PMF, and the proposed criteria for PPV-MF and PET-MF outlined by the International Working Group for Myeloproliferative Neoplasms Research and Treatment (IWG-MRT) (see Appendix 2) irrespective of *JAK2* mutation status. A bone marrow biopsy will provide the relevant information; subjects without a prior biopsy report obtained in the 2 months prior to screening for review must have a biopsy at screening or baseline or will not be able to enroll in the study.
4. Subjects with MF requiring therapy must have at least 1 point using the DIPSS prognostic criteria developed by the IWG-MRT (Passamonti et al 2010), using the information from laboratory assessments and ongoing medical history recorded at the screening visit. The prognostic variables and assigned point values are:

| Prognostic Variable | Value | | |
|--------------------------------------|---------------------------|---------------------------|-----------|
| | 0 Points | 1 Point | 2 Points |
| Hemoglobin ^a | ≥ 10 g/dL | | < 10 g/dL |
| Age, Years | < 65 | ≥ 65 | |
| White Blood Cell Count | ≤ 25 x 10 ⁹ /L | > 25 x 10 ⁹ /L | |
| Peripheral Blood Blasts | < 1% | ≥ 1% | |
| Constitutional Symptoms ^b | No | Yes | |

^a A hemoglobin value < 10 g/dL must be demonstrated during the screening visit for subjects who are not transfusion dependent. Subjects receiving at least 2 units of packed red blood cells in the 12 weeks prior to Screening will be considered to have hemoglobin < 10 g/dL for the purpose of evaluation of risk factors.

^b Constitutional symptoms are defined as any of the following: 10% or more weight loss in the 6 months prior to screening, night sweats, unexplained fever (> 37.5°C).

5. Subjects in whom treatment of MF is indicated based on the Investigator's expert judgment.
6. Subjects with active symptoms of MF at the screening Visit as demonstrated by presence of one symptom score of at least 5 or two symptom scores of at least 3 using the Screening Symptom Assessment Form ([Appendix 7](#)).
7. Subjects who have platelet counts between 50 and 100 x 10⁹/L at the screening and/or baseline visits. Platelet counts must be without the assistance of growth factors, thrombopoietic factors, or platelet transfusions.
8. Subjects with hemoglobin value at the screening visit ≥ 6.5 g/dL and who are willing to receive red blood cell transfusions to treat low hemoglobin levels.
9. Subjects must have discontinued all drugs used to treat underlying MF disease no later than Day -14.
10. Subjects must not currently have the option of stem cell transplantation, either because they are not a candidate, or because a suitable donor is not available.
11. Subjects with an ECOG performance status of 0, 1, 2 or 3 ([Appendix 5](#)) at the screening visit.
12. Subjects with peripheral blood blast count of < 5% at both screening and baseline visits.

6.3. Subject Exclusion Criteria

Any of the following are causes for exclusion from the study, and must be demonstrated not to be present at the screening visit (historical data for measurements or labs may not be used):

1. Subjects with a life expectancy of less than 6 months.
2. Subjects in whom MF disease is well controlled with current therapy.
3. Females who are pregnant or are currently breastfeeding.
4. Subjects of childbearing potential who are unwilling to take appropriate precautions (from screening through follow-up) to avoid becoming pregnant or fathering a child.
 - Females of non-childbearing potential are defined as women who (a) are ≥ 55 years of age with history of amenorrhea for 1 year, OR (b) are surgically sterile for at least 3 months.
 - For females of childbearing potential, or for males, appropriate precautions are those that are at least 99% effective in preventing the occurrence of pregnancy. These methods should be communicated to the subjects and their understanding confirmed ([Appendix 3](#)).
5. Subjects with inadequate bone marrow reserve as demonstrated by:
 - Absolute neutrophil count (ANC) that is $< 1 \times 10^9$ /L at the screening or baseline visits **or** had ANC levels $< 500/\mu\text{L}$ in the month (30 days) prior to screening. Subjects must not have received growth factors for at least 1 month (30 days) prior to receiving the first dose of study drug.

- Confirmed platelet count that is $< 50 \times 10^9/L$ or subjects with a known history of platelet counts $< 25,000/\mu L$, in the absence of cytoreductive therapy.
6. Subjects with platelet count $> 100 \times 10^9/L$ at BOTH screening and baseline visits.
 7. Subjects with recent (within 12 months of screening) major bleed requiring transfusion(s) or resulting in a decrease in hemoglobin by 3 g/dL or more.
 8. Subjects with inadequate coagulation parameters as follows: INR > 1.5 or PTT $> 1.5 \times$ upper limit of laboratory normal (ULN).
 9. Subjects with known history of esophageal or gastric varices, or any intracranial bleeding. Subjects with a history of an incidental finding of small varices (< 5 mm) may be permitted in the study with Sponsor approval.
 10. Subjects with inadequate liver or renal function at screening and baseline visits as demonstrated by:
 - Direct bilirubin $\geq 2 \times$ ULN (NOTE: direct bilirubin will only be determined if total bilirubin is $\geq 2.0 \times$ ULN).
 - Alanine aminotransferase (ALT)/aspartate aminotransferase (AST) $> 2.5 \times$ ULN.
 - Serum creatinine > 2.0 mg/dL or creatinine clearance < 30 mL/min measured or calculated by Cockcroft-Gault Equation.
 11. Subjects with clinically meaningful, active bacterial, fungal, parasitic or viral infection which require therapy, or who are HIV positive
 12. Subjects with acute bacterial infections requiring antibiotic use should delay screening/enrollment until the course of antibiotic therapy has been completed and the event is considered resolved.
 13. Subjects who are currently receiving therapy with a moderate or potent CYP3A4 inhibitor ([Appendix 8](#)). Subjects may enter the screening phase when therapy with the moderate or potent CYP3A4 inhibitor is completed, and use of moderate inhibitors during the study will be permitted.
 14. Subjects with an invasive malignancy over the previous 2 years except treated early stage carcinomas of the skin completely resected intraepithelial carcinoma of the cervix and completely resected papillary thyroid and follicular thyroid cancers.
 15. Subjects with recent severe or unstable cardiac disease.
 16. Subjects who have had splenic irradiation within 6 months prior to Day 1.
 17. Subjects who have previously received treatment with a JAK inhibitor.
 18. Subjects being treated concurrently with any prohibited medications (see [Section 8.9.2](#) for specific prohibited medications and the associated timeframe over which they are prohibited).
 19. Subjects with active alcohol or drug addiction that would interfere with their ability to comply with the study requirements.

20. Subjects with any concurrent condition that, in the investigator's opinion, would jeopardize the safety of the subject or compliance with the protocol.
21. Subjects who are unable to complete the daily symptom diary, which is available in English and Spanish versions.

6.4. Subjects Who Fail to Meet Screening Criteria

A subject who has a laboratory test result(s), vital signs, or ECG finding(s) that does not satisfy the entrance criteria may have the test(s) repeated once. These tests may be repeated as soon as the investigator believes that the retest result is likely to be within the acceptable range to satisfy the entrance criteria, but must be completed within the 3 week screening phase (Days -28 to -8). In this case, the subject will not be required to sign another ICF, and the original subject identification number will be used. In the event that the laboratory test(s) cannot be performed within the screening period, or the re-test(s) do not meet the entrance criteria or the subject's medical condition has changed significantly during the screening phase so that inclusion/exclusion criteria are no longer met, the subject is considered a screen failure, and must be withdrawn from the study. Therefore, sites should consider the testing schedule carefully so that any potential retests are accomplished in the 3 week time frame. If the subject and investigator agree to re-screening, the subject must sign a new ICF, a new subject identification number will be assigned, and all required screening activities must be performed when the subject is re-screened for participation in the study (except bone marrow biopsy if already performed at screening). An individual subject may only re-screen once for the study.

If all screening activities cannot be completed in the screening phase because of an event unrelated to a laboratory finding, ECG finding, or medical history finding, including scheduling difficulties at the clinic site, the subject may retain the original subject number and complete the remaining screening activities as soon as possible, within a maximum of 42 days (6 weeks) from the original screening visit date. A blood draw for hematology and serum chemistry must be taken at the time the subject returns for completion of screening activities, and will be used to determine eligibility.

7. INVESTIGATIONAL PLAN

7.1. Overall Study Design

This is an open label study of ruxolitinib in patients with PMF, PPV-MF, and PET-MF. The study is comprised of 4 phases:

| | |
|----------------------------------|--|
| Screening: | Up to 21 days |
| Baseline: | Exactly 7 days |
| Core Treatment Phase: | 24 weeks |
| Extended Treatment Phase: | 132 weeks; subjects receiving benefit will continue ruxolitinib treatment until Week 156 |
| Follow-up Phase: | All subjects will be followed for safety (eg, reporting of AEs and SAEs) for 30 to 37 days after the last dose of study drug is administered |

Core Treatment Phase:

During the core treatment phase, there will be study visits and laboratory-only visits. Subjects will have a regularly scheduled study visit at screening, baseline, Day 1, Week 4, Week 8, Week 12, Week 16, Week 20 and Week 24, where blood samples, assessments, spleen measurements, etc. will be obtained. All hematology labs and coagulation parameters will be analyzed by local laboratories. Serum chemistries, serology, and lipid panel will be analyzed by a central laboratory.

Subjects will have laboratory-only visits to collect hematology lab samples at Week 1, Week 2, Week 3, Week 5, Week 6, Week 7, Week 10, Week 14, and Week 18. The laboratory visits at Week 14 and Week 18 may be skipped for subjects who do not increase their dose at Week 12 or Week 16, and who have maintained platelet counts $> 75 \times 10^9/L$ since the last hematology assessment. Additional, at least weekly laboratory-only visits to collect hematology lab samples will be required if platelet count falls below $35 \times 10^9/L$; more frequent monitoring is recommended if counts fall below $25 \times 10^9/L$. These laboratory visits can occur at the study site laboratory, or any local laboratory that can provide the data and appropriate certificates and normal laboratory ranges to the study site for review for subject management in a timely fashion.

Subjects will have an MRI of the upper and lower abdomen and pelvis to determine the spleen volume at baseline and Week 24. A CT scan will be substituted for subjects who are not candidates for MRI, or when MRI is not readily available. Patients Global Impression of Change (PGIC) questionnaire will be completed monthly. Measurement of spleen length below the left costal margin will be measured by palpation at each study visit.

Subjects will complete an electronic symptom diary from baseline through the Week 24 visits (total of 25 weeks). Subjects will be trained on the use and care of the diary, and symptom diary data will be transmitted automatically each night wirelessly or using the diary docking station provided to subjects.

Extended Treatment Phase:

Subjects will have a study visit every 12 weeks (eg, Weeks 36, 48, 60, 72, 84, 96, 108, 120, 132, 144, and 156), through Week 156 where blood samples, clinical assessments, and palpable spleen measurements, etc. will be obtained. Subjects will have laboratory-only visits to collect hematology samples 6 weeks after the Week 24 visit (eg, Week 30), then after **each** extended treatment phase visit (eg, Weeks 42, 54, 66, 78, 90, 102, 114, 126, 138, and 150). Additional hematology assessments will be required if the subject has a dose modification or as clinically indicated.

Follow-Up Phase:

All subjects will be followed for safety (eg, reporting of AEs and serious AEs) for 30 to 37 days after the last dose of study drug is administered.

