8.6.1. Dose Increases

Dose increases are optional.

During the core treatment phase, doses of ruxolitinib may be increased in 5 mg qd increments up to a dose of 10 mg bid starting at the Week 4 visit and at subsequent study visits. Dose increases can occur no more frequently than every 4 weeks, and only if:

- Platelet count was always $\geq 40 \times 10^9/L$ since the last scheduled study visit
- Platelet count, if decreased since the last scheduled study visit, is decreased by no more than 20% of the platelet count at the last scheduled visit
- No dose decreases or holds for safety have occurred during the preceding 4-week interval
- $ANC > 1.0 \times 10^9/L$ since the last scheduled study visit.
- For subjects with prior \geq Grade 2 hemorrhage events, please see below under [Section 8.6.3.4](#), Restarting with Resolution of Hemorrhage Events

Doses may not exceed 10 mg bid except in subjects who continue to meet the above dose escalation criteria, and who have, in addition, a PGIC score of 3 (minimally improved) to 7 (very much worse) while receiving 10 mg bid. Such subjects may continue dose escalation to a maximum dose of 15 mg bid. Note that when a 5 mg qd increment is added, creating a regimen such as 5 mg/10 mg, the higher dose should be taken in the evening and the lower dose in the morning.

During the extended treatment phase, doses of ruxolitinib may be increased in 5 mg qd increments up to a dose of 25 mg bid if the subject meets the above dose escalation criteria, or per the investigator's discretion.

Doses may never exceed 25 mg bid.

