12.2. Statistical Analyses

12.2.1. Primary Analyses

Co-Primary Endpoints:

- Correlation of % change in spleen volume at Week 24 compared to baseline versus final titrated dose.
- Correlation of % change in Total Symptom Score as measured by the modified MFSAF v2.0 diary at Week 24 compared to baseline versus final titrated dose.

The null hypothesis is that the correlation between percent change in spleen volume or total symptom score and final titrated dose is zero. The test will be based on the t test for a product-moment correlation coefficient:

$$t = r_{xy} \sqrt{(n - 2) / (1 - r_{xy}^2)}$$

(Cohen 1988, Formula 3.1.1)

A two-sided alpha of 5% will be used. With a sample size of 150, the critical correlation that is needed to reject H_0 is 0.16. If the absolute value of the observed correlation is 0.16 or higher, H_0 will be rejected. In order to keep the overall alpha at 5%, a sequential testing procedure will be used: First we will test the correlation with % change in spleen volume, and only if the null hypothesis of no correlation can be rejected will we continue to test the correlation with % change in Total Symptom Score.

Safety Endpoints:

Safety and tolerability will be assessed by monitoring the frequency, duration and severity of adverse events, performing physical examinations, collecting vital signs, collecting laboratory data for hematology, serum chemistry, coagulation parameters, and lipid panel through Week 156.

Change in platelet count from baseline to each visit where the variables are measured will be tabulated with summary statistics.

Proportion of subjects with new onset of Grade 4 thrombocytopenia events, and proportion of subjects with new onset of Grade 2 or higher hemorrhage, as measured by CTCAE will be tabulated with summary statistics. The hazard functions of time to onset of the above two safety measures will be estimated using life table method.

Adverse events will be tabulated by the Medical Dictionary for Regulatory Activities (MedDRA[®]) preferred term and by system organ class. Severity of AEs will be based on the CTCAE scale as indicated in [Section 11.1.1](#).

The subset of AEs that are considered by the Investigator to be related to study drug will be considered to be treatment-related AEs. If the Investigator does not specify the relationship of the AE to study drug, the AE will be considered to be treatment-related. The incidence of AEs and treatment-related AEs will be tabulated.

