## **8.2. Laboratory Values**

Clinical laboratory tests including hematology, serum chemistry, coagulation, and urinalysis will be performed for each subject during the study in accordance with the Schedule of Observations (see [Table 3](#)). If specific safety issues arise, additional, unscheduled laboratory tests/analyses may be performed at the discretion of the investigator.

All test results and associated normal ranges from central laboratories will be reported in Standard International units (SI unit). All tests with numeric values will have a unique unit per test. Any laboratory results and associated normal ranges from local laboratories will be converted to SI units. When there are multiple laboratory values for a subject’s particular test at a given visit, the last non-missing value will be used in the by-visit tabulations and summaries described below.

Numeric laboratory values will be summarized descriptively, and non-numeric test values will be tabulated by study visit using data collected from scheduled visits.

For those tests with available normal ranges, the number and percentage of subjects with the laboratory values being low, normal, or high will be calculated for each test. A shift summary will be produced, which presents the change from baseline as shown in [Table 5](#).

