14.3.1.2.1	Subject Laboratory Value over Time: Platelet (GI/L)	Safety
14.3.1.2.2	Mean (95% CI) Laboratory Value Over Time: Platelet (GI/L)	Safety
14.3.1.3.1	Subject Laboratory Value over Time: WBC (GI/L)	Safety
14.3.1.3.2	Mean (95% CI) Laboratory Value Over Time: WBC (GI/L)	Safety
14.3.1.4.1	Subject Laboratory Value over Time: Neutrophil (GI/L)	Safety
14.3.1.4.2	Mean (95% CI) Laboratory Value Over Time: Neutrophil (GI/L)	Safety

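### Observed platelet means at Weeks 14 and 18 will tend to be too low, because the subjects allowed to skip those two samples are the ones with higher counts

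*Protocol*

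**What the plan says.** Protocol 7.1 lists Weeks 14 and 18 among the laboratory-only hematology visits and then makes them conditional: "The laboratory visits at Week 14 and Week 18 may be skipped for subjects who do not increase their dose" at Week 12 or 16 and "who have maintained platelet counts $> 75 \times 10^9/L$ since the last hematology assessment". Both conditions must hold. The synopsis, the footnotes to Table 4 and section 9.2 repeat the rule. The study visits on either side have no such option: "Week 12, Week 16, Week 20 and Week 24, where blood samples, assessments, spleen measurements, etc. will be obtained". Section 8.6.1 adds: "Dose increases are optional".

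On analysis, Protocol 12.2.1 commits to this: "Change in platelet count from baseline to each visit where the variables are measured will be tabulated with summary statistics". SAP 8.2 says: "Numeric laboratory values will be summarized descriptively, and non-numeric test values will be tabulated by study visit using data collected from scheduled visits". SAP 5.6 assigns laboratory values to nominal weeks. SAP Table 3 shows Weeks 14 and 18 as ordinary scheduled hematology visits with no note on skipping. SAP 10.2 lists Figure 14.3.1.2.2, "Mean (95% CI) Laboratory Value Over Time: Platelet (GI/L". The SAP's laboratory text mentions neither the skip rule nor any handling of the values it leaves out.

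**The concern.** At Weeks 14 and 18 the set of subjects contributing a platelet value is selected on recent platelet count. Those with lower counts, and those whose dose was just raised, must attend; those with higher counts on a stable dose may stay away. A mean taken over whoever attended is then compared, in the same table row or on the same curve, with Weeks 12, 16 and 20, where everyone is sampled. With no true change the display would tend to fall at Weeks 14 and 18 and recover at Weeks 16 and 20.

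The platelet course is a central safety description in a trial enrolling at 50 to 100 x 10^9/L, and dosing strategy is a secondary objective. The two weeks come directly after the Week 12 and 16 dose-increase visits, and Protocol 4.1.5 says most subjects had reached 10 mg BID at Week 13. A selection dip there is easily read as a dose effect.

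**Working it through.** The plan states no figure on this point, so there is nothing to reproduce. The check is of direction first, then size.

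**Direction.** Let s be the fraction skipping and g the amount by which the skippers' Week 14 mean would exceed the full-cohort mean. The observed mean is low by

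dip = s x g / (1 - s).

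This is positive whenever someone skips and g > 0.

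**Inputs from the documents.** Threshold 75 x 10^9/L; selection on counts before the skipped visit; dose raisers may not skip.

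**Assumed inputs, not in the documents.** Normal counts with mean m and SD d of 60/18, 65/20 or 70/22; correlation 0.8 between the qualifying count and the Week 14 count; 30% of those above 75 raise dose, at random; uptake u among eligible subjects of 25%, 50% or 100%; 120 subjects with data.

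**Formulas.** z = (75 - m)/d; p = P(Z > z); s = p x 0.7 x u; g = 0.8 x d x phi(z)/p, with phi the standard normal density; SE = d/sqrt(120).

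**Worked case (65/20, u = 50%).** z = 0.5, p = 0.309, phi = 0.352, g = 0.8 x 20 x 0.352/0.309 = about 18.3. s = 0.309 x 0.7 x 0.5 = 0.108. Dip = 0.108 x 18.3/0.892 = 2.2.

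| Mean/SD | p above 75 | g | Dip, u=25% | Dip, u=50% | Dip, u=100% | SE |
|---|---|---|---|---|---|---|
| 60/18 | 0.202 | 20.1 | 0.7 | 1.5 | 3.3 | 1.64 |
| 65/20 | 0.309 | 18.3 | 1.0 | 2.2 | 5.0 | 1.83 |
| 70/22 | 0.410 | 16.7 | 1.3 | 2.8 | 6.7 | 2.01 |

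In standard errors of the full mean this runs from 0.74/1.64 = 0.45 to 6.72/2.01 = 3.35. At 50% uptake it is 0.9 to 1.4.

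**Sensitivity.** A simulation with lognormal counts (mean 70, SD 20, correlation 0.8 on the log scale, 30% raising dose) gave dips of 1.1, 2.4 and 5.6 at 25%, 50% and 100% uptake. With SD 30 they were 1.6, 3.6 and 8.3, so a wider spread takes the all-skip case above 7.

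**Change from baseline.** With baseline uniform on 50 to 100, 30% raising dose and a true mean change of -7.6, the observed mean change was -8.5, -9.5 and -12.1 at the three uptakes. The excess fall is 0.9, 1.9 and 4.5.

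**When the sign fails.** The dip reversed in one contrived setting: overall mean 90, with dose raisers being exactly the upper half of those above 75. The full mean was 90.0, the skippers' mean 86.3 and the observed mean 91.9. That is an unlikely pattern for subjects enrolled at 50 to 100 on a platelet-lowering drug.

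**The case against.** The strongest reply is that this is a caveat on descriptive output at two time points. Skipping is optional, and if nobody skips there is no bias. SAP 5.4.1 requires the number of observations, so a drop in n would be visible. The named safety proportions are Grade 4 thrombocytopenia, counted from any value below 25 GI/L, and Grade 2 or higher hemorrhage. CTCAE shift tables use all scheduled and unscheduled data, and individual platelet plots and a longitudinal PK-PD platelet analysis are also planned. No figure shells are supplied, so it is not stated that the mean curve includes laboratory-only weeks. Removing the two weeks outright would cost information just after dose-increase visits and would cut across the commitment in Protocol 12.2.1.

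Most of this stands, and it limits the scope and shapes the remedy. It does not remove the bias: a smaller n shows that values are missing but not that they are the higher ones, and the other analyses do not correct this table or figure.

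Three stronger readings are tempting and are not supported:
- A reader might infer that the mean curves for hemoglobin, WBC and neutrophils are biased in the same way. The rule selects on platelets and dose only, and no bias has been shown for the other three.
- A reader might remove everyone whose Week 14 or 18 count itself exceeds 75, and so get a larger dip (70.1 to 64.7 with half removed and 55.6 with all removed, at mean 70, SD 22). The rule uses earlier counts and excludes dose raisers, and both features shrink the effect.
- A reader might call any observed fall spurious. Dose raisers must attend and are over-represented, so part of it may be a real drug effect.

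**Conclusion.** The point holds for platelets. As planned, observed by-visit platelet means and mean changes from baseline at Weeks 14 and 18 will tend to be too low relative to Weeks 12, 16 and 20. The direction follows from the skip rule in any plausible setting with some uptake. The size cannot be found from the documents; under the assumptions above it ranges from below one standard error at 25% uptake to about two to three if every eligible subject skips. The co-primary correlations, the Grade 4 analysis and the CTCAE shift tables do not depend on these means. This is a modest interpretive risk in a safety display, worth preventing because prevention is nearly free.

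**What to change.** In SAP 8.2 and Figure 14.3.1.2.2, state that Weeks 14 and 18 are not joined to the mean platelet curve. Draw the curve from weeks at which the sample is required of all subjects, or replace it with a mixed-model estimate using all platelet data; the model is reasonable because skipping depends on observed counts and recorded dose changes.

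Keep the observed Week 14 and 18 platelet values in Table 14.3.3.1.1, which honours Protocol 12.2.1. Show n and the number of permitted skips, with a footnote that the sample is selected on prior platelet count and dose. Leave these values in the shift tables and individual-subject plots. The hemoglobin, WBC and neutrophil figures need no change on this ground.

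The cost is SAP wording and programming. No data are lost, but the mean curve gives up two points shortly after dose-increase visits, or needs one extra model.
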